#### 17.4.2.2 Re-infection with a different genotype of P.aeruginosa

#### 17.4.2.2.1 Derivation

This outcome is derived using the Microbiology CRF, and includes only samples taken at or after  $T_3$  or at or before  $T_{15}$ . A binary variable: *P.aeruginosa* infection with a different genotype of *P.aeruginosa* is defined as: genotype of at least one re-infection sample  $\neq$  genotype of baseline infection sample, Yes/No. Where the genotype of the baseline sample is unknown / not available, it will not be possible to derive this outcome.

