## **17 Efficacy Evaluations**

## 17.1 Data sets analysed

The principle of intention-to-treat, as far as practically possible, will be the main strategy of the analysis adopted for the primary outcome and all the secondary outcomes. These analyses will be conducted on all randomised participants, in the group to which they were allocated, and for whom the outcome(s) of interest have been observed/measured. No imputations will be made.

The membership of the analysis set for each outcome will be determined and documented and reasons for participant exclusion will be given prior to the blind being broken and the randomisation lists being requested. Reasons may include missing data, loss to follow up.

Participants to be excluded from analysis populations will be defined in template ST001TEM04: Protocol deviations and data set definitions, agreed and approved prior to any release of randomisation code.

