#### Update following blind review:

Two analyses of this outcome will be performed. The first analysis will assume that all patients who do not have both a baseline sample and a follow up sample in the time window of interest (T3 to T24) sent for genotyping did not have a reoccurrence of the original *P.aeruginosa* strain (E=0). The second analysis will assume that these patients did have the original *P.aeruginosa* strain reoccur (E=1).

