#### 17.4.2.2.2 Analysis

The number and percentage of patients who are infected with a different type of *P.aeruginosa* during the first 12 months post treatment phase will be presented (from  $T_3$  to  $T_{15}$ ), split by treatment group. The denominator is the total number of patients within each treatment arm for whom the outcome is derivable. The relative risk together with 95% confidence interval will be reported along with a two-sided p-value from a chi-squared test. The Fisher's exact test may be used if the chi-squared test is not appropriate (counts of <5 within categories).

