## **18 Missing Data and Withdrawals**

Explicit derivations above give methods for handling missing data and withdrawals regarding derivation of outcomes. Section 14.2 above describes how withdrawals will be reported.

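### The different-genotype re-infection outcome drops certain non-events, leaves ungenotyped regrowth undefined, and has no analysis for missing genotypes

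*SAP*

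**What the plan says.** SAP 17.4.2.2.1 defines a Yes/No variable from samples between T3 and T15. It is Yes when the "genotype of at least one re-infection sample" differs from the genotype of the baseline sample. One ground for non-derivability is given: "Where the genotype of the baseline sample is unknown / not available, it will not be possible to derive this outcome".

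SAP 17.4.2.2.2 then states: "The denominator is the total number of patients within each treatment arm for whom the outcome is derivable". On the comparison it says: "The relative risk together with 95% confidence interval will be reported along with a two-sided p-value from a chi-squared test", with Fisher's exact test as a fallback for small counts.

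Three other places bear on the point.

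- Section 17.1 restricts each analysis to participants in their allocated group "and for whom the outcome(s) of interest have been observed/measured. No imputations will be made".
- Section 18 adds no rule of its own: "Explicit derivations above give methods for handling missing data and withdrawals regarding derivation of outcomes".
- Under time to reoccurrence of the original infection (17.4.2.1.2), the update after the blind review says "Two analyses of this outcome will be performed". It begins: "The first analysis will assume that all patients who do not have both a baseline sample and a follow up sample in the time window" sent for genotyping had no reoccurrence; the second analysis assumes that they did. The change log records this for 17.4.2.1.2. Its only entry for 17.4.2.2.2 removes a repeat of the analysis by genotype.

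**The concern.** Two kinds of patient are not handled well.

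- **No baseline genotype and no *P. aeruginosa* from T3 to T15.** Without regrowth there can be no re-infection with a different strain, so the answer is a certain No. The derivation still calls the outcome non-derivable and makes no exception. Known non-events leave the denominator.
- **Baseline genotyped, organism regrown, follow-up isolate not genotyped.** The strain is unknown. The binary rule finds no sample shown to differ and so returns No, whereas 17.1 suggests that the outcome was not observed and the patient is excluded. Two programmers could produce different results from the same SAP.

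The blind review provided for patients who lack one or both genotyped samples. Time to reoccurrence and this outcome both need the same two genotypes, yet only the former received bounding analyses. At stake are the two reported rates, a relative risk and a p-value for one secondary outcome.

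**Working it through.** The SAP gives no rate, sample size or genotyping completeness for this outcome, so there is no figure to reproduce. All values below are assumptions that show how the rules behave.

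**Notation**, per arm:

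- *r*: risk of regrowth from T3 to T15
- *s*: share of regrowers with a different strain
- *b₁*, *b₀*: probability that the baseline genotype is available in regrown and never-regrown patients
- *g*: probability that the follow-up isolate is genotyped

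**Formulas**

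- True risk = *r s*
- Literal reading (ungenotyped regrowth is No) = *r b₁ g s* / [*r b₁* + (1−*r*) *b₀*]
- 17.1 reading (ungenotyped regrowth excluded) = *r b₁ g s* / [*r b₁ g* + (1−*r*) *b₀*]

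**Results**, IV v oral. Unless stated, *r* = 0.45 v 0.55 and *s* = 0.4, so the true risks are 18% v 22% and the true RR is 0.18/0.22 = 0.818.

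| Assumed completeness | Literal reading | 17.1 reading |
|---|---|---|
| A. Baseline 80%, follow-up 70%, same in both arms | 12.6% v 15.4%, RR 0.818 | 14.6% v 18.4%, RR 0.79 |
| B. Baseline 80%, follow-up 80% v 60% | 14.4% v 13.2%, RR 1.09 | 15.8% v 16.9%, RR 0.94 |
| C. As B, but *r* = 0.5 in both arms (true 20% each, RR 1) | 16% v 12%, RR 1.33 | 17.8% v 15.0%, RR 1.19 |
| D. Baseline typed only if regrown, follow-up complete | 40% v 40%, RR 1.00 | 40% v 40%, RR 1.00 |
| E. Baseline 90% if regrown and 40% if not, follow-up 80% | 20.7% v 23.5%, RR 0.88 | 23.8% v 27.5%, RR 0.87 |
| F. Baseline 80% at random, follow-up complete | 18% v 22%, RR 0.818 | 18% v 22%, RR 0.818 |

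Example, row A, IV arm. Literal: 0.45×0.8×0.7×0.4 / (0.45×0.8 + 0.55×0.8) = 0.1008/0.80 = 12.6%. Under 17.1: 0.1008 / (0.252 + 0.44) = 14.6%.

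The two readings differ wherever follow-up typing is incomplete (A, B, C, E). On the literal reading the rates fall but the RR holds if completeness is equal across arms (A); the RR moves if completeness differs by arm (B, C). The baseline rule does no harm if missingness is unrelated to regrowth (F). If baseline typing depends on regrowth, it distorts the rates, and the RR too when regrowth differs by arm (D, E).

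**Bounds.** Keep every sampled patient without regrowth as No, and set unclassifiable regrowth to all No or all Yes:

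- lower = *r b₁ g s*
- upper = *r b₁ g s* + *r*(1 − *b₁ g*)

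For row B:

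- IV: 0.45×0.8×0.8×0.4 = 0.1152; upper 0.1152 + 0.45×0.36 = 0.2772
- Oral: 0.55×0.8×0.6×0.4 = 0.1056; upper 0.1056 + 0.55×0.52 = 0.3916
- RR, all No: 0.1152/0.1056 = 1.09; all Yes: 0.2772/0.3916 = 0.71
- Crossed: 0.1152/0.3916 = 0.29 and 0.2772/0.1056 = 2.63

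The arm limits, 11.5–27.7% and 10.6–39.2%, contain the true 18% and 22%. The crossed pair gives the outer limits for the RR. In row D nothing is unclassifiable, and the bounds collapse to 18% v 22%, RR 0.818.

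**The case against.** A reader might infer that the plan scores ungenotyped regrowth as No and thereby biases both the rates and the relative risk. The documents do not support that. The derivation names one situation in which the outcome cannot be derived and does not say that it is the only one. The definition compares two genotypes, and without one of them the comparison cannot be made. The derivable denominator and the observed-outcome rule in 17.1 support exclusion at least as well. Section 17.1 also requires analysis-set membership and reasons for exclusion to be documented before the randomisation lists are requested. Nor is bias in the relative risk certain: rows A (literal reading) and F show none, and nothing in the SAP says that completeness differs by arm. Excluding every patient without a baseline genotype treats regrown and never-regrown patients alike, which is defensible when that missingness is random.

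All of this stands, and it limits the point to an undefined rule and a possible bias. It does not remove the gap. Section 18 relies on the derivations to handle missing data, and this one covers only the baseline genotype. Excluding ungenotyped regrowth under 17.1 is not neutral either: in row A it moves the RR from 0.818 to 0.79.

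The obvious repair, keeping all never-regrown patients and dropping unclassifiable regrowth, can be worse than the present rule because inclusion then depends on the outcome. Take 40% regrowth, half of it a different strain (true 20%), baseline typed at random in 80% and follow-up complete. The SAP rule gives 0.16/0.80 = 20%. The repair gives 0.16/(0.32 + 0.60) = 17.4%. With baseline complete and follow-up typing of 90% v 60%, the repair gives 18/(36 + 60) = 18.8% v 12/(24 + 60) = 14.3%, RR 1.31 for a true RR of 1.

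**Conclusion.** The concern holds in limited form. As written, 17.4.2.2.1 removes certain non-events when the baseline genotype is missing. It does not fix the handling of ungenotyped regrowth, and the outcome has no analysis for missing genotypes, although the plan provides one for its companion outcome. The rates can be biased. The relative risk can be biased if genotyping completeness differs by arm, or if baseline typing depends on regrowth. The distortions above, such as RR 1.33 for a true 1 or RR 1.00 for a true 0.818, rest wholly on assumed completeness; the SAP does not allow the actual size or direction to be stated. The point concerns one secondary outcome and does not touch the primary analysis. It merits a cheap correction before the randomisation lists are requested.

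**What to change.** 1. In 17.4.2.2.1, state that regrowth between T3 and T15 with a missing baseline or follow-up genotype, and no isolate shown to differ from baseline, is unclassifiable and is not scored No by default. Report its count by arm.
2. In 17.4.2.2.2, extend the extreme-case approach of 17.4.2.1.2 to this outcome with two analyses. In both, every patient sampled from T3 to T15 without regrowth is No whatever the baseline genotype. Unclassifiable regrowth is set to No in one and Yes in the other. Only regrown patients are varied.
3. Also report the relative risk with unclassifiable regrowth set to Yes in one arm and No in the other, and the reverse. The all-No and all-Yes pair alone does not give the outer limits of the ratio.
4. Do not adopt a main analysis that keeps all never-regrown patients but drops unclassifiable regrowth. It selects on the outcome and lowers the rates.

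The cost is a few sentences in the SAP, a little more programming and wider reported uncertainty on a secondary outcome. No new data are needed.

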#### 17.4.2.2.2 Analysis

The number and percentage of patients who are infected with a different type of *P.aeruginosa* during the first 12 months post treatment phase will be presented (from  $T_3$  to  $T_{15}$ ), split by treatment group. The denominator is the total number of patients within each treatment arm for whom the outcome is derivable. The relative risk together with 95% confidence interval will be reported along with a two-sided p-value from a chi-squared test. The Fisher's exact test may be used if the chi-squared test is not appropriate (counts of <5 within categories).

#### 17.4.2.3 Lung function – FEV1, FVC, FEF25-75

According to the protocol, spirometry is not routinely carried out in those under 5 years of age although the global lung function initiative states it is valid for patients aged 3-95. To avoid confusion, only participants aged 5 or older will be included in this analysis.

#### 17.4.2.3.1 Derivation

Three raw spirometry measurements FEV1, FVC, and FEF25-75 are taken at each visit. These are recorded at baseline (CRF: *Baseline*, Variables: BLFEV1R, BLFVCR and BLFEV25I); at follow-up (CRF: *Follow-up*, Variables: FUFEV1R, FUFVCR and FUFEV25I); and at unscheduled visits (CRF: *Unscheduled Visit*, Variables: UVFEV1R, UVFVCR and UVFEV25I).

For the purpose of this analysis, all available lung function measurements will be included.

These are converted to clinically useful measures: %predicted FEV1, %predicted FVC, and %predicted FEF25-75 using a SAS macro available from the global lung initiative [7] which requires as input the participants' raw measurements, their age at the visit (derived from date of visit: FUVISITD or UVVISITD and date-of-birth: FUDOBD or UVDOBD), and their height at the visit (for scheduled visits, this is recorded in FUHGHTR; for unscheduled visits height is not recorded – therefore height should be taken from the closest scheduled visit CRF).

A time variable (days from randomisation) will be derived as Visit Date minus Randomisation Date.

#### 17.4.2.3.2 Analysis

#### % predicted FEV1 (%PredFEV1)

Summary statistics (total [n], mean, SD, median, interquartile range, range, minimum and maximum) will be presented split by treatment at three key time-points:  $T_3$ ,  $T_{15}$  and  $T_{24}$ . Only data from scheduled visits at these time-points will be included.

A repeated measures random effects model will be fitted. The dependent variable will be post baseline %PredFEV1. Covariates will be: baseline %PredFEV1, treatment group, time and an interaction term (treatment group\*time). A special power covariance structure will be used, under the assumption that the correlation between repeated measurements weakens the greater the time between measurements.

Co-efficients from the model will be presented and a single p-value will be reported testing whether the effect of treatment group is significant over the whole follow-up period.

The mean (SE) %PredFEV1 at 3 months, 15-months and 24 months with 95% confidence intervals as predicted by the fitted model will be reported for each treatment group. The mean

difference between the two treatment groups in %PredFEV1 at 15 months will be presented together with a 95% CI.

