#### 17.4.2.9.2 Analysis

For each of the 23 domains:

A mixed-effects model for repeated measures will be fitted, with an unstructured covariance matrix. The baseline measurement of the domain will be fitted as a covariate along with *Form prepared:* 20/06/2018 v1.0 *for TORPEDO-CF Study* 

treatment group, time-point as a categorical variable and an interaction term (treatment group\*time). The following will be reported: mean (SD) for each treatment group; mean (95% CI) difference between treatment groups at  $T_{15}$  (derived from the model); and a p-value of the treatment effect. A plot of mean (SE) for each time-point, by treatment group will be presented.

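### The lung-function model appears to tie each arm's mean, and the T15 difference, to a straight line in time; use a categorical or flexible time term instead

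*SAP*

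**What the plan says.** SAP section 17.4.2.3.1 defines the time scale: "A time variable (days from randomisation) will be derived as Visit Date minus Randomisation Date". It also decides which data enter: "For the purpose of this analysis, all available lung function measurements will be included". That includes unscheduled visits.

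Section 17.4.2.3.2 sets the model. "The dependent variable will be post baseline %PredFEV1", and "Covariates will be: baseline %PredFEV1, treatment group, time and an interaction term" of treatment with time. The correlation is to decay with elapsed time: "A special power covariance structure will be used, under the assumption that the correlation between repeated measurements weakens the greater the time between measurements" (presumably the spatial power structure). The reported outputs are "The mean (SE) %PredFEV1 at 3 months, 15-months and 24 months with 95% confidence intervals as predicted by the fitted model", and the arm difference at 15 months with a 95% CI. No visit factor, polynomial, spline or check of linearity is given.

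The same analysis is applied to FVC, FEF25-75, O2 saturation, the three child z-scores and adult BMI. With FEV1 that makes eight outcomes. For CFQ-R, section 17.4.2.9.2 instead specifies "time-point as a categorical variable and an interaction term".

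Section 8.9 places scheduled post-baseline visits every 12 weeks from T3 (week 12) to T24 (week 96). Patients randomised after 1 January 2016 were followed to T15 only.

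**The concern.** The planned outputs belong to particular time-points. The change-control table records that blind review moved the reporting of this outcome to specific time-points. A model with one slope per arm does not estimate T3, T15 and T24 separately. It fits two parameters for the arm difference and reads all three values off that line.

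If the difference is curved after T3, for example an early benefit that fades or a late one that emerges, values at other visits leak into the T15 estimate. The patients followed to T24 add to this, because their later visits help set the slope for everyone. The quantity at risk is the one between-arm estimate with an interval that the plan names for each of these outcomes.

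**Working it through.** The SAP gives no effect size, SD or sample size for lung function, so there is no figure of its own to reproduce. The calculation shows how the specified mean model handles a non-linear difference.

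**Inputs from the SAP.** Visits at days 84, 168, 252, 336 and 420 (T3 to T15), then 504, 588 and 672 (T18 to T24), from section 8.9. These run from treatment start and are taken here as days from randomisation. The mean model and the decaying correlation are those of section 17.4.2.3.2.

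**Assumptions.** n = 100 per arm, residual SD 10, correlation 0.7 per 84 days, complete data at the stated visits, and a true difference d of +4 at T3 and 0 at every later visit.

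**Formulas.** X has rows (1, t). V = (2 × 10²/100) × R, with R = 0.7^(|t_j - t_k|/84).

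- Expected fitted difference at t: x_t'(X'V⁻¹X)⁻¹X'V⁻¹d.
- Standard error: √[x_t'(X'V⁻¹X)⁻¹x_t].
- Coverage of the 95% CI: Φ(1.96 - b/SE) - Φ(-1.96 - b/SE), where b is the bias.

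Only the T3 value of d is non-zero, so each fitted value is 4 times the weight given to the T3 visit.

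| Visits | Time | Weight on T3 | Fitted | True | SE | Coverage |
|---|---|---|---|---|---|---|
| T3–T15 | T3 | 0.828 | +3.31 | +4 | 1.39 | 92% |
| T3–T15 | T15 | -0.138 | -0.55 | 0 | 1.39 | 93% |
| T3–T24, all followed | T3 | 0.706 | +2.82 | +4 | 1.34 | 86% |
| T3–T24, all followed | T15 | 0.200 | +0.80 | 0 | 0.96 | 87% |
| T3–T24, all followed | T24 | -0.180 | -0.72 | 0 | 1.34 | 92% |

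For the fourth row, b/SE = 0.80/0.956 = 0.84, and Φ(1.12) - Φ(-2.80) = 0.87. In that case the T15 visit itself carries a weight of only 0.08 in the T15 estimate. T3 carries 0.20 and T24 carries 0.33.

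**Other correlation.** At 0.9 per 84 days the T15 value is -0.25 with visits to T15, but +1.26 (coverage 82%) with all followed to T24. High serial correlation does not protect the estimate.

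**Other shapes.** These take a 5-point effect, half the sample followed to T24 and correlation 0.95 per 28 days:

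- Linear decline to 0 at T24: bias 0.00 at T3, T15 and T24.
- 5 points through T6, then 0: fitted +1.13 at T15 (true 0) and -1.48 at T24 (true 0).
- 0 until T9, then 5: fitted 3.62 at T15 (true 5).

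In these 5-point scenarios with nobody followed past T15, the T15 bias lay between 0 and about -0.4.

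**The case against.** **Linearity is inferred.** The SAP never uses the word for this model. That is correct, and the plan cannot be said to state a linear trend. But days over irregular visit dates cannot sensibly be a class variable, and no other functional form is given. If another form was meant, the SAP needs to say so.

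**A reader might infer that a change of slope at T3 is built in because treatment ends about then.** The documents do not support that as the main argument. The outcome is post-baseline and scheduled visits start at T3, so only unscheduled or early visits fall before it. What matters is curvature after T3, and the SAP gives no expectation about that either way.

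**A reader might call the CFQ-R model an internal contradiction.** It is not one. CFQ-R is collected at a few fixed time-points, whereas spirometry is also recorded at unscheduled visits, and section 8.9 reports many visits outside their windows. That is a fair reason to want continuous time. It is not a reason to want a straight line.

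**Raw summaries at T3, T15 and T24 are also planned.** They could reveal misfit, but they do not correct the model-based means or the T15 interval, and no fallback is specified.

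**The sizes rest on assumptions.** True: n, SD, correlation, effect and shape are all assumed, and only part of the sample has visits after T15.

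**Conclusion.** The point stands as an inexpensive improvement to secondary analyses. On its natural reading, the model makes the T3, T15 and T24 means and the T15 difference collinear in time. Under the stated assumptions, a 4-point difference confined to T3 moves the T15 estimate by -0.55 to +0.8 points, depending on whether follow-up stops at T15 or everyone reaches T24. Coverage at T15 is 93% and 87% respectively.

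The stronger conclusion, that the T15 results are biased, does not follow. The bias is zero if the difference is linear and small at T15 if nobody is followed past T15. Its actual size cannot be learned from the SAP. The primary outcome is not affected.

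**What to change.** For all eight outcomes using section 17.4.2.3.2, state the form of time and choose one of two options:

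- **(a) Categorical.** Enter scheduled time-point as a factor with a treatment by time-point interaction. Assign assessments by prespecified date windows reconciled with section 8.9. Do not let unscheduled values from the treatment phase, or values triggered by illness, count as T3 to T24. Assigning each value to its nearest visit would do exactly that.
- **(b) Flexible.** Keep all measurements and continuous days, but use a prespecified flexible function of time interacted with treatment, for example a restricted cubic spline with knots after T3.

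In either case keep actual days for the power covariance, and take the T3, T15 and T24 means and the T15 difference from this model. A single knot at day 84 would not help: it leaves T3 to T24 linear, and on the scheduled grid it is collinear with the intercept and slope (rank 2 of 3 columns), so the fitted values do not change.

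The cost is SAP wording, a small programming change, a windowing or knot rule, and some precision. With visits to T15, the categorical T15 SE is √(2 × 100/100) = 1.41 against 1.39. With everyone followed to T24 the gap is larger, 1.41 against 0.96, because the narrower interval there is bought by assuming linearity. The form should be fixed before outcome data are analysed by arm.

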#### 17.2 Demographic and other baseline characteristics

Summary statistics for baseline variables will be calculated for the ITT dataset, split by treatment group to check that randomisation has worked – i.e. that the treatment groups are balanced. Baseline characteristics to be summarised are described in Tables 1 and 2. Table 1 details continuous baseline variables to be reported, and Table 2 details categorical baseline variables.

Categorical data will be summarised by numbers and percentages. Continuous data will be summarised by total (n), mean and SD. Tests of statistical significance will not be undertaken; rather the clinical importance of any imbalance will be noted.

Note: Known reasons for missingness of baseline data will be summarised.

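### Models that adjust for baseline lose randomised patients who have follow-up values but no baseline, and the SAP gives no rule for keeping them

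*SAP*

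**What the plan says.** Section 17.1 sets the analysis on all randomised participants as allocated, "and for whom the outcome(s) of interest have been observed/measured. No imputations will be made". Having a baseline value is not a stated condition. The same section qualifies the principle ("The principle of intention-to-treat, as far as practically possible, will be the main strategy of the analysis") and provides for exclusions from each outcome's analysis set, documented before the randomisation lists are requested: "Reasons may include missing data, loss to follow up".

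For lung function, 17.4.2.3.1 says that every available measurement is to be used. In 17.4.2.3.2 the response is the post-baseline value, and "Covariates will be: baseline %PredFEV1, treatment group, time and an interaction term". FVC, FEF25-75, oxygen saturation (17.4.2.4.2), child height, weight and BMI z-scores and adult BMI (17.4.2.5.2) all refer back to this model. For each of the 23 CFQ-R domains, 17.4.2.9.2 says: "The baseline measurement of the domain will be fitted as a covariate".

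The SAP foresees missing baselines. Section 17.2 says "Known reasons for missingness of baseline data will be summarised", and 17.4.2.3 notes that "spirometry is not routinely carried out in those under 5 years of age". Section 18 refers missing data back to the outcome derivations, and none of them covers a missing baseline.

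**The concern.** A mixed model handles missing responses but not missing covariates. With baseline as a covariate and no imputation, every follow-up record of a patient without a baseline is deleted, however many such records there are. The patients in the model are then not those that the opening definition in 17.1 describes, nor all those whose lung-function measurements 17.4.2.3.1 says will be used. For the FEV1-type outcomes, the descriptive summaries at T3, T15 and T24 need no baseline, so the summary and the model printed beside it could rest on different patients without explanation.

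What is at stake is precision in eight FEV1-type models and 23 CFQ-R models, and a clear statement of who is analysed.

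**Working it through.** The SAP gives no sample size and no count of missing baselines, so there is no stated figure to reproduce. The inputs below are assumptions, shown over a range.

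**Inputs.** m is the share of patients with follow-up data who lack a baseline: 5%, 10%, 20%. r is the baseline/follow-up correlation: 0.5, 0.7, 0.8. The algebra takes one follow-up value per patient, equal arms and baseline missing at random. The residual variance, in units of the outcome variance, is 1 − r² with baseline and 1 without.

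**Step 1: what can be recovered.** Information per patient is 1/(1 − r²) with baseline and 1 without. Complete cases give (1 − m)/(1 − r²). Keeping the other patients at their proper weight adds m, so

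gain = m(1 − r²)/(1 − m).

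Example, r = 0.8 and m = 10%: 0.10 × 0.36/0.90 = 4.0%.

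**Step 2: mean fill plus indicator with one common residual variance.** All patients are now weighted equally, so the variance of the treatment effect is proportional to (1 − m)(1 − r²) + m, against (1 − r²)/(1 − m) for complete cases.

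Example, r = 0.8 and m = 10%: 0.90 × 0.36 + 0.10 = 0.424 against 0.36/0.90 = 0.400. The information ratio is 0.400/0.424 = 0.943, a loss of 5.7%.

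| r | Method | m = 5% | m = 10% | m = 20% |
|---|---|---|---|---|
| 0.5 | proper weighting | +3.9% | +8.3% | +18.8% |
| 0.5 | common variance | +3.5% | +7.5% | +17% |
| 0.7 | proper weighting | +2.7% | +5.7% | +12.7% |
| 0.7 | common variance | +0.4% | +1.4% | +4.9% |
| 0.8 | proper weighting | +1.9% | +4.0% | +9.0% |
| 0.8 | common variance | −3.3% | −5.7% | −7.8% |

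With proper weighting and a gain g, the standard error falls by 1 − 1/√(1 + g): about 1-2%, 2-4% and 4-8% at the three values of m.

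**Step 3: break-even for the common-variance version.** Setting (1 − r²)/(1 − m) equal to (1 − m)(1 − r²) + m gives 1 − r² = (1 − m)/(2 − m). At m = 5%, 10%, 20% this is 0.487, 0.474, 0.444, so r = 0.72, 0.73, 0.75. Above that, adding the patients this way widens the interval.

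**Step 4: the age route.** T15 is at 60 weeks: 60 × 7/365.25 = 1.15 years. If the age limits are judged at the visit, a child aged about 3.85 to under 5 at baseline can have spirometry by T15 without a routine baseline, and one aged about 4.85 to under 6 can have CFQ-R. At T24 (96 weeks, 1.84 years) the bands start at about 3.16 and 4.16. If the limits are judged at entry, these children are outside the analysis by design and this route closes.

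**The case against.** The strongest reply is that 17.1 already covers this. It applies intention-to-treat only as far as practical, and it lists missing data among the possible reasons for exclusion, provided that membership is documented in advance. A reader might infer that the models contradict 17.1. The text does not support that, because a documented exclusion for missing baseline would comply. What survives is narrower. Section 17.1 ties membership to the observed outcome, no section names missing baseline as an exclusion reason, and 17.4.2.3.1 says that all lung-function measurements are used. Keeping these patients is also practicable, so the qualifier does not require losing them.

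A second reply is that baseline-adjusted complete-case analysis is legitimate and that the extent is unknown. That stands. Height, weight and oxygen saturation are scheduled at baseline, and nothing in the SAP points to material missingness there. The note in 17.2 is general and implies no rate.

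A third reply is that a simple mean fill can do harm. That also stands, as Step 2 shows, and it decides which remedy is acceptable.

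**Conclusion.** The point holds as a gap with a modest cost. As specified, randomised patients with post-baseline values but no baseline fall out of all these models, and the SAP neither says so nor provides for them. The recoverable information is about 2-4%, 4-8% and 9-19% at an assumed 5%, 10% and 20% missing, for r between 0.5 and 0.8. Both ranges are assumptions, and the formula simplifies a repeated-measures model to one follow-up value. Only secondary outcomes are affected; the primary analysis uses no baseline covariate.

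Two further inferences are tempting and not supported. One is that the treatment comparison is biased: nothing in the SAP shows this. The other is that the loss falls mainly on young children. That depends on judging the limits of 5 and 6 years at the visit, and the SAP does not say whether they apply at entry or at the visit.

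**What to change.** In 17.4.2.3.2 (which carries over to 17.4.2.4 and 17.4.2.5) and in 17.4.2.9.2, state that every patient with at least one post-baseline value stays in the model, by one of two methods:

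- Place baseline in the response vector with a mean common to both arms, in place of the baseline covariate. The treatment and treatment-by-time terms then apply to post-baseline values only.
- Fill a missing baseline with the mean of both arms pooled, add a missing-baseline indicator, and allow that group its own residual variance/covariance.

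Do not use mean fill with a single common variance, for the reason shown in Step 3. In 17.1, limit the bar on imputation to outcomes; if the second method is chosen, name the baseline fill as the exception. State also whether the age limits for spirometry and CFQ-R apply at entry or at the visit.

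The cost is a few sentences, slightly more complex model code and, with the second method, a stated exception to the no-imputation rule. The filled value is a pre-randomisation covariate and uses no treatment information. If the sponsor prefers complete cases, the minimum is to name missing baseline as an exclusion reason in 17.1 and to report the number excluded by arm for each model.
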